Sixth Step--Baseline phase, all 30 phrases (see attachment 1) will be tested using the phrase completion task (see attachment 2). Both correct responses and participation will be verbally reinforced. Results will be analyzed by the ST to ensure that the sets are of equal difficulty for each participant. (Expected length of time 5 visits or 2 weeks)

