Seventh Step--Intervention phase (B) (see flowchart attached), each song (music with lyrics) from set 1 (B1 songs #1-10) will be played in its entirety. When the targeted verse or chorus plays, the written lyrics will be simultaneously shown along with the song lyrics. The ST will point to the words of the targeted verse/chorus which will be silently observed by the participant as they are sung. This will be repeated for all 10 songs. The phrase completion task will then be presented, including the ten phrases from the songs played that day and the five control phrases, without music. The participant will silently or orally read the phrase and orally read and/or circle or point to the phrase completion choice. Correct responses will be verbally reinforced. The next session, each song (music with lyrics) from set 2 (B2 songs #11-20) will be played in its entirety. After the song plays, the written lyrics from the targeted verse or chorus will be presented. The ST will point to the words of the targeted verse/chorus which will be silently observed by the participant. This will be repeated for all 10 songs. The phrase completion task will then be presented, including the ten phrases played that day and the five control phrases. The participant will silently or orally read the phrase and orally read and/or circle or point to the phrase completion choice. Correct responses will be verbally reinforced. This will be repeated for all 10 songs. For all interventions, the number of correct responses will be tallied on a LaPoint Base 10 form and the percent correct will be entered on the graph for that day. The same procedures will be repeated, alternating procedures on sets 1 and 2 on subsequent treatment visits, until a criterion of 9/10 (90%) x 3 consecutive visits is reached on both sets. If the criterion is not reached on one of the intervention sets, defined as no increase in percentage correct x 3 consecutive visits, a correction procedure will be applied using modeling of the correct response. If the criterion still is not reached, that intervention will be determined to be limited in effectiveness and discontinued. Every third session will be videotaped for a reliability check by the recruiter/research team member. When both of the sets (B1 and B2) have been acquired or one acquired and the other discontinued, the number of sessions to criterion will be counted for each intervention. (Expect length of time 2- 12 weeks)

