Eighth Step--Posttest BDAE-3 full version Reading subtests (extended posttest). (Expected length of time one visit)

Ninth Step--Retest retention of 30 phrases 3-week follow-up. (Expected length of time one visit)

Total number of visits: 16-48; total length of time 10-20 weeks per patient.

For CFMH or Roanoke Day Rehab, the PI, who is also the treating SLP, will make clear to subjects each time when standard therapy has ended and a research study intervention is about to begin. The subjects will be told approximately how long the research intervention is expected to take. For CRMH Inpatients, research will be separated in time and completed by a different SLP (the PI).

7. **Data Collection:** Attach a copy of your data collection tool or spreadsheet listing exactly what data is to be gathered during this research study. Describe below the data collection methods and how data be compiled for assessment.

Outcome Measures and Time Points

Pretest/post-test information on the ICF Body Functions/Structures, Activities, and Participation will be provided (Hurkmans et al. 2011).

The Boston Diagnostic Aphasia Examination (BDAE) (Goodglass, Harold, & Kaplan, 1983): Pretest reading scores on the BDAE full version subtests, i.e. B. Word Identification: 1. Word-Picture Match, and 2. Lexical Decision; C. 1. Homophone Matching; D. Derivational and Grammatical Morphology: 1. Matching to spoken sample; E. Oral Reading: 1. Basic oral word reading; F. Oral Reading of Sentences with Comprehension; and G. Reading Comprehension-Sentences and Paragraphs; will be completed prior to baseline A and initiating intervention, and immediately following completion of intervention to assess generalization to non-trained stimuli.

At three weeks follow-up the trained stimuli from all three interventions will be retested to assess retention (see Flow Diagram).

The dependent variables, i.e. differential response to the two interventions (counted as the percent correct responses per day, number of sessions required to achieve mastery at each level (simple counting), retention of the material (number of items remembered).

Reporting Participant Characteristics

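### The intervention step accounts for 25 of the 30 phrases tested at baseline and follow-up, and the control set's size, testing schedule and retention score are not defined consistently

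*Combined protocol and SAP*

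**What the plan says.** Section 6 (Methodology) gives the phrase counts step by step.

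- Sixth Step, baseline: "all 30 phrases (see attachment 1) will be tested using the phrase completion task".
- Seventh Step, simultaneous sessions: "each song (music with lyrics) from set 1 (B1 songs #1-10) will be played in its entirety". The test that follows is described as "including the ten phrases from the songs played that day and the five control phrases, without music".
- Seventh Step, priming sessions: "each song (music with lyrics) from set 2 (B2 songs #11-20) will be played in its entirety". The test is described as "including the ten phrases played that day and the five control phrases".
- Seventh Step, progression: "alternating procedures on sets 1 and 2 on subsequent treatment visits, until a criterion of 9/10 (90%) x 3 consecutive visits is reached on both" (that is, on set 1 and on set 2).
- Ninth Step: "Retest retention of 30 phrases 3-week follow-up".

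Section 4 (Study Design) has the control set used in one session out of three, as a check on change due to time or outside events. Section 7 (Data Collection) defines the daily measure as a percentage, but the follow-up measure as "retention of the material (number of items remembered". Section 8 (Statistical Analysis) compares the control with both music conditions on sessions to mastery and on three-week retention. Attachment 1, which lists the phrases, is not in the text available for review.

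**The concern.** The control is the only part of the design that shows what happens to these phrases without music. For that it needs a known set of items, a known testing schedule, and a score on the same footing as the music sets. The body of the plan settles none of the three. Five phrases are measured at baseline and follow-up with no stated place in the intervention phase. The control schedule is given in two incompatible ways. The retention score is a count whose maximum depends on a set size that is not stated.

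Each test is also practice, because correct answers are praised. Unequal testing per phrase can therefore move the control relative to the music sets for reasons unrelated to music. The comparisons at stake are those of each music condition with control in section 8.

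**Working it through.** **1. Phrase count.** Set 1 has 10 phrases (songs 1 to 10), set 2 has 10 (songs 11 to 20), and the control has 5 at each session. 10 + 10 + 5 = 25, which is 30 − 25 = 5 short of the stated total. A control set of ten would give 10 + 10 + 10 = 30, but the text nowhere says this.

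**2. Tests per phrase.** Let S be the number of intervention sessions while both sets alternate. Each music phrase is tested S/2 times. Counts below are for S = 12; the ratios do not depend on S.

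| Reading | Tests per control phrase | Tests per music phrase | Ratio |
|---|---|---|---|
| Same five, every session (section 6): S | 12 | 6 | 2.0 |
| Same five, one session in three (section 4): S/3 | 4 | 6 | 0.67 |
| Five of ten in rotation, every session: S/2 | 6 | 6 | 1.0 |
| Five of ten in rotation, one session in three: S/6 | 2 | 6 | 0.33 |

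Only the third reading gives equal practice, and the plan does not describe it. The ratios change once one music set is acquired or discontinued.

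**3. Session score.** One item is worth 100/5 = 20 points for control and 100/10 = 10 points for a music set. Treating items as independent with a common probability p correct, the standard error is 100 × √(p(1 − p)/n). At p = 0.5 it is 22.4 points for n = 5 and 15.8 for n = 10, a ratio of √2 = 1.41.

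**4. Mastery criterion.** The rule is 9/10 (90%). Five items give 4/5 = 80% or 5/5 = 100%, never 90%, so a requirement of at least 90% becomes 5/5. At an assumed p = 0.9, the chance of meeting it on one day is 0.9⁵ = 0.59 for control against 10 × 0.9⁹ × 0.1 + 0.9¹⁰ = 0.74 for a music set. At p = 0.5 the order reverses: 0.031 against 0.011. Sessions to mastery for control would not be on the same scale.

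**5. Retention count.** If the control set is five, the maxima are 5 for control and 10 for each music set. If it is ten with a fixed five used in sessions, both maxima are 10, but the control count mixes five repeatedly tested phrases with five untested since baseline. Simultaneous against priming is 10 against 10 on either reading.

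**The case against.** The strongest reply is that the control set is probably ten and attachment 1 would show it. Thirty phrases with two sets of ten leave ten; the Seventh Step tallies all interventions on a base-10 form; and section 7 speaks of three interventions at follow-up. This is plausible and cannot be ruled out. But both session types refer to the five control phrases as if they were one fixed group. Even if the list holds ten, the procedure does not say which five are used or whether they rotate.

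Several stronger inferences are tempting, and the documents do not support them.

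- A reader might infer that five phrases serve no purpose. All 30 are tested at baseline and follow-up; what is missing is a stated role in the intervention phase.
- A reader might infer that control phrases are tested twice as often, biasing the music effect toward nothing. That follows only from section 6 with a fixed five. Under section 4 the ratio is 0.67 and the bias could run the other way.
- A reader might infer that control is measured less precisely overall. The loss is per session. With a fixed five over 12 sessions, control gives 12 × 5 = 60 responses and each music set 6 × 10 = 60. The planned trend and control-limit analyses use the series, not single days.
- A reader might infer that unequal denominators affect every outcome. Daily scores are already percentages, and the retention hypothesis, which sets simultaneous against priming, compares ten items with ten.

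**Conclusion.** The point holds for the control comparison. The text leaves 5 of 30 phrases unexplained in the intervention phase and contradicts itself on how often the control is tested. With a fixed five, practice per control phrase is 2.0 or 0.67 times that of a music phrase, depending on which section is followed, so neither equality nor the direction of bias can be assumed. Control retention is either out of 5 against 10, or out of 10 with practised and unpractised phrases mixed.

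The ratios assume that both music sets are still alternating and that the same five control phrases recur. Attachment 1 could settle the set size, but not the conflict between sections 4 and 6. The comparison of the two music procedures on retention stands as planned. The plan should be corrected before enrolment; this does not call the whole design into question.

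**What to change.** 1. State the size of the control set, in agreement with attachment 1 and the total of 30.
2. Reconcile sections 4 and 6 on how often the control is tested.
3. If the set is ten, present five at each control administration in a preset balanced order. Each pair of administrations should cover all ten, with the split into fives redrawn by a preset list so that it is not tied to either music condition. The order should continue if one music set is discontinued. Practice per control phrase then matches a music phrase as closely as the reconciled schedule allows.
4. If the set is five, say what the other five phrases are for and leave them out of control retention. Practice stays unequal under either stated schedule, so report tests per phrase by condition.
5. Report retention as percent of set for all three conditions. Say whether sessions to mastery is computed for control and, if so, by what rule on five items.

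The cost is procedure wording and revised task sheets, with no added phrases or visits. One limitation remains: each control score still rests on five items, so the control should be read over pairs of administrations.

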The main neurological structures that must remain intact for the proposed treatment to work are lateralized left hemispheric, i.e. left amygdala and left extrastriate cortex. While it seems intuitive to choose patients with right cerebral vascular accident (CVA) as the trial subjects, deeper analysis of the fMRI results reveals that areas on the right middle and superior temporal gyri and bilaterally the superior parietal gyrus post central were simultaneously activated. In addition, it has been shown that reading comprehension is bilaterally organized. For example, Hauk et al. revealed that words are processed by distributed neuronal networks that reflect word semantics (Hauk, Johnsrude, & Pulvermuller, 2004). Specifically, event-related fMRI showed that action words/verbs presented in passive reading differentially activated areas in the motor strip involved in the actual movements. Further, the left hemispheric structures involved in re-entrant processing are not part of the primary speech/language areas, i.e. Broca's, conduction, or Wernicke's areas. Therefore, the population of subjects who could most benefit from the proposed treatment should be those with localized cortical aphasia.

Because the identification of the intact targeted structures, i.e. left amygdala to left extrastriate cortex, is the basis for inclusion in this study, signs/symptoms defining injury to those neuro-anatomical structures should also be the basis of exclusion criteria. Type of aphasia need not be a limiting factor. In single-subject research design, each subject serves as his/her own control, so severity levels need not be defining criteria, because the effect on the outcomes of both treatments would be the same. Hemianopsia or other visual field defects, unilateral hemi-neglect or inattention affecting vision for reading need to be excluded, and in particular right homonymous hemi- or inferior quadrantanopsia which would indicate a lesion of the left parietal or temporal lobes and involvement of the left optic radiations.

Inclusion Criteria

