AT CRCH Inpatient Rehab treating SLPs, which does not include the researcher, will inform patients of the study and ask at a standard speech therapy session if the patient and legally authorized representative or person of the patient's choosing would agree to meet, via Carilion Secure Videoconferencing, with the Rehab Director to discuss the possibility of being in a research study. The treating SLP will notify the recruiter of the patient's decision. If the patient/representative agree, then a mutually agreeable time will be scheduled.

At Roanoke Day Rehab the PI may or may not be the treating therapist. If the PI is the treating speech therapist, procedures to CFMH Outpatient will be followed. If the PI is not the treating therapist, procedures will mirror those used at CRCH Inpatient Rehab. The PI will set up the conference call but will not be present in the meeting, unless requested to come back in to assist given any problem with equipment. (Expected length of time one visit).

Third Step--Informed consent interview with SLP outside the patient's normal treatment time. SLP researcher will review consent document with patient and patient's representative. The informed consent discussion is expected to take 45 to 60 minutes. Patient will answer yes/no comprehension questions regarding the information presented, which will be documented in writing by the SLP researcher. Any questions answered in error will prompt a review of the information by the SLP. If the patient scores less than an average of 80% on the yes/no comprehension test after the review,

the patient will not be asked to participate in the study. Patient will have three days to review consent document at home and make a decision. (Expected length of time one visit plus three days)

Fourth Step--Administer pretest Boston Diagnostic Aphasia Examination (BDAE-3) full version Reading subtests (extended testing). (Expected length of time one visit)

Fifth Step--All songs will be pretested for familiarity and positive valence by questioning the participants (i.e. do you know this song? Do you like it?). Response data will be recorded. (Expected length of time 1-2 visits)

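### As written, song set 1 always gets simultaneous presentation and set 2 always gets priming, so hypotheses 3 to 5 cannot be separated from song set

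*Combined protocol and SAP*

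**What the plan says.** Section 6, Seventh Step, describes one sequence. In the first session, "each song (music with lyrics) from set 1 (B1 songs #1-10) will be played in its entirety", and the written words appear while the target verse or chorus is sung. In the following session, "each song (music with lyrics) from set 2 (B2 songs #11-20) will be played in its entirety", and the written words come after the song. The step then continues by "alternating procedures on sets 1 and 2 on subsequent treatment visits" until both sets reach 9/10 on three consecutive visits. Sessions to criterion are counted per intervention once sets B1 and B2 are acquired, or one is acquired and the other discontinued. The step opens with "Intervention phase (B) (see flowchart attached"; that chart was not available for this review, nor were attachments 1 and 2.

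Two earlier steps bear on whether the sets are comparable. Fifth Step: "All songs will be pretested for familiarity and positive valence by questioning the participants". Sixth Step: "Results will be analyzed by the ST to ensure that the sets are of equal difficulty for each participant". Neither gives a tolerance, a matching rule or a rule for moving phrases between sets.

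Hypotheses 3, 4 and 5 (section 3) state that simultaneous presentation will beat priming on effectiveness, efficiency and retention. Section 5 asks for four to ten participants. Section 8 compares sessions to mastery and three-week retention across the two music conditions and the control, then forms group means after at least four completers.

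**The concern.** If every participant learns songs #1-10 by one procedure and songs #11-20 by the other, procedure and song set are the same variable. A set whose phrases are easier to learn or remember would produce the pattern the hypotheses predict, or hide a real effect, and the data could not show which had happened.

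The plan's defence is that "each subject serves as his/her own control, so severity levels need not be defining criteria". That covers what belongs to the participant, such as severity. It does not cover what belongs to the training material. Replication, the usual protection in a single-subject design, does not help either, because each replication repeats the same pairing. The abstract gives finding the most effective and efficient method as the purpose, and that choice rests on this contrast. Hypotheses 1 and 2 do not rest on set 1 versus set 2 and are less affected.

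**Working it through.** **The plan's own figure.** The only sample-size figure is the minimum of four, justified by a textbook citation. It has no formula inputs, so there is nothing to reproduce.

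**1. Is the contrast identifiable?** Take a model with one effect per participant, one for procedure and one for song set.

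- Pairing as written: rank 5 of 6 columns with four participants, 11 of 12 with ten; the procedure-set correlation is 1.0. The effects cannot be separated at either size.
- Half the participants reversed: rank 6 of 6 and 12 of 12; correlation 0. The variance factor for procedure is 0.50 with four and 0.20 with ten, the same as in a model without set.

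With procedure effect *t* and set effect *s*, the pairing as written estimates *t + s*. Reversing half gives (*t + s*)/2 + (*t − s*)/2 = *t*.

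**2. What can the baseline check detect?** With 10 phrases per set over 5 visits and independent responses, the SE of the set difference in one participant is √(2 × mean[p(1−p)] / 50).

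- All phrases at p = 0.5: √(0.5/50) = 10.0 points. At p = 0.3 or 0.7: √(0.42/50) = 9.2 points.
- Half the phrases at 0.8 and half at 0.2: √(0.32/50) = 8.0 points. At 0.9/0.1: √(0.18/50) = 6.0 points.

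At 10.0 points the 95% half-width is 1.96 × 10.0 = 19.6 points. The check also measures starting difficulty only, not speed of learning or retention.

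**3. How large could the bias be in sessions?** All inputs here are assumptions. Probability correct at session *s* is 0.97 − 0.62·exp(−r(s−1)), with 10 items per session and mastery as the plan defines it. There is no procedure effect. The sets learn at r(1+d) and r(1−d), so d = 0.05, 0.10 and 0.20 make one set 11%, 22% and 50% faster than the other (for example 1.10/0.90 = 1.22). The three values of r give 8.6, 11.3 and 15.8 sessions per set. Two sets plus 12-13 other visits is about 29 to 45 visits, inside the stated 16-48.

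| Sessions per set | False difference, d = 0.05 | d = 0.10 | d = 0.20 | SD of four-participant mean (d = 0.10) |
|---|---|---|---|---|
| 8.6 | 0.48 | 0.96 | 1.97 | 1.35 |
| 11.3 | 0.70 | 1.41 | 2.91 | 1.75 |
| 15.8 | 1.09 | 2.17 | 4.47 | 2.37 |

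- At d = 0.10, bias/SD is 0.96/1.35 = 0.7, 1.41/1.75 = 0.8 and 2.17/2.37 = 0.9. With ten completers the SD is multiplied by √(4/10), and the ratios become 1.1, 1.3 and 1.4.
- Adding participant-specific variation in d (SD 0.20) to a shared 0.10 gives 1.1, 1.6 and 2.5 sessions against SDs of 1.8, 2.5 and 3.6. If the gap is wholly participant-specific, the bias is 0.0.
- The chance that all four participants need fewer sessions on the faster set is 3-4% with no gap, 10-16% at d = 0.10 and 25-40% at d = 0.20. That pattern would look like replication.
- With half the participants reversed, the mean difference is 0.0 in every cell at an unchanged SD.

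**4. Does the plan's correction rule change this?** The trigger is "defined as no increase in percentage correct x 3 consecutive visits, a correction procedure will be applied". It was modelled with correction assumed to have no effect. At d = 0.10 the difference where both sets are acquired is 0.96, 1.40 and 2.10 sessions. The slower set triggers correction in 7%, 19% and 41% of cases, against 4%, 13% and 31% for the faster set, so the alias also reaches that outcome.

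**5. Retention.** With an assumed average of 70%, a full gap between sets of 5, 10 or 20 points is 0.5, 1.0 or 2.0 items out of 10. The SD of the four-participant mean is √(2 × 10 × 0.7 × 0.3 / 4) ≈ 1.0 item.

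**The case against.** - **The flowchart may settle it.** It is where an assignment scheme would naturally appear, and its absence here is not a fault in the plan. This stands in full as a condition on the conclusion.
- **The wording about alternating procedures could mean a swap between sets.** It could, but the sentence says the same procedures are repeated, and session counts per intervention are read from B1 and B2. A fixed pairing is the likelier reading; the ambiguity itself needs removing.
- **The baseline check might involve re-sorting phrases for each person.** That would turn much of a shared gap into participant-specific variation, which averages to zero. No such rule is stated, and the songs are numbered into fixed sets. The check and the song pretest do make a large starting imbalance less likely.
- **The illustrated bias is modest.** At d = 0.10, already a 22% difference in learning rate, it is smaller than chance noise with four participants. At d = 0.05 it is about 0.35 to 0.46 SD. Ten completers is the upper extreme, since ten is requested to allow for attrition. All of this is right and limits the urgency.
- **The primary objective in section 3 does not name superiority over priming.** True. The point concerns hypotheses 3 to 5 and the purpose stated in the abstract, not whether the new treatment works at all.

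**Conclusion.** The concern holds on the text available. Hypotheses 3 to 5 are completely aliased with song set, and neither more participants nor group means remove the part of a set difference that participants share. The alias follows from the design and needs no assumption beyond the fixed pairing. Its size depends on set differences the plan does not give: about 1.0 to 2.2 sessions at d = 0.10, 0.5 to 1.1 at d = 0.05, zero if gaps are wholly participant-specific, and in either direction. It should be fixed because the remedy is cheap, not because a large bias has been shown. Confidence is medium, since the flowchart and attachments could already resolve it.

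**What to change.** If the flowchart already counterbalances the sets, say so in one sentence of the Seventh Step. Otherwise:

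- **Seventh Step.** Use a list generated before enrolment in blocks of two. In each block one participant gets set 1 simultaneous and set 2 priming, and the other gets the reverse. Starting with set 1 in both groups also balances which procedure comes first; as written, simultaneous always starts, a smaller confound of the same kind. Reword the alternation sentence so that the pairing within a participant is unambiguous.
- **Section 8.** Report the simultaneous-minus-priming difference by assignment group, average the two groups with equal weight for hypotheses 3 to 5, and keep the individual graphs. Where a set is discontinued there is no session count to criterion, so report discontinuations by assignment group too.

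The cost is protocol wording and a short list, with the same songs, sessions and participants. The therapist must follow a per-participant assignment. Set and procedure stay confounded within each person, so individual graphs may disagree between groups. Equal weighting needs at least one completer per group and loses some precision when completers are unbalanced. With a 3/1 split at d = 0.10 and about 11 sessions per set, the simple mean keeps 0.7 of the 1.4 sessions of bias (SD 1.76); equal weighting removes it at an SD of 2.04.
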